4.2 Exclusion Criteria

A subject who meets any of the following criteria is not eligible:

- 1. Did not complete a minimum of 3 months of AR101 Maintenance in the parent study if subject was assigned to AR101 in that study, except for subjects in ARC004 who did not tolerate the nondaily AR101 dosing regimen, subjects in ARC007 or ARC010, or unless specified otherwise in the parent study
- 2. History of chronic disease (other than asthma, atopic dermatitis, or allergic rhinitis) that is, or is at significant risk of, becoming unstable or requiring a change in chronic therapeutic regimen, including malignancies occurring within 5 years prior to Screening and clinically active autoimmune diseases
- 3. Subjects with a history of alcohol, illicit or recreational drug or prescribed medication abuse
- 4. Developed a clinically significant change in health status during the parent study that, in the opinion of the investigator, would make the subject unsuitable for participation in this study
- 5. Taking a prohibited medication, as listed in Section 5.9.5, except during the follow-up observation period in this study
- 6. Currently participating in any other interventional clinical study other than the Aimmune parent study, except during the follow-up observation period in this study
- 7. Currently receiving or received within 5 years prior to Screening any type of peanut or other food allergen immunotherapy, except AR101 or unless allowed in the parent study, and except during the follow-up observation period in this study
- 8. Subject is living in the same household or is a dependent of sponsor employee and/or site staff involved in conducting this study, except for subjects originating from Aimmune Studies ARC002, ARC004, ARC007, ARC010, and ARC011
- 9. Currently in the build-up phase of immunotherapy for any non-food allergen, except during the follow-up observation period in this study
- 10. Hypersensitivity to epinephrine or hypersensitivity to any of the excipients in the investigational product (IP)
 - 11. Pregnant or breastfeeding
- 12. Inability to withhold antihistamines for 5 half-lives prior to the initial day of escalation or visits at which an SPT or food challenge is conducted
- 13. Discontinued early from the parent study for any safety reason, except a subject from study ARC004 who has experienced a lack of tolerance for a nondaily dosing regimen, and subjects who discontinued early from an eligible parent study due to AEs (including chronic or recurrent GI AEs) who require continued safety follow-up only
- 14. Currently committed to an institution (eg, psychiatric institution, prison) by virtue of an order issued by judicial or administrative authorities
- 15. Any other condition that, in the opinion of the investigator, precludes participation for reasons of safety
- 16. Subjects unable to follow the protocol requirements

4.3 Screen Failures

A screen failure is defined as a subject who consents or a subject whose parent/guardian consents to participation in the study but does not meet the eligibility criteria.

4.4 Early Discontinuation

A subject may discontinue dosing with AR101 anytime if the investigator determines that continuation in the study is detrimental to the subject. Following early discontinuation, subjects will return to the clinic to complete the End of Treatment visit.

Early discontinuation procedures may be affected by a pandemic, epidemic, or other emergency not related to the study as described in Appendix 12.

4.4.1 Criteria for Early Discontinuation

A subject who meets any of the following must discontinue dosing with AR101:

- 1. Pregnancy
- 2. Life-threatening symptoms (CoFAR grade 4; Appendix 9), including, but not limited to anaphylaxis resulting in hypotension, neurologic compromise, or mechanical ventilation secondary to peanut OIT dosing or any peanut food challenge
- 3. Severe allergic hypersensitivity symptoms (CoFAR grade 3; Appendix 9) that require intensive therapy (to be determined by the investigator but may include such interventions as IV epinephrine, intubation, or admission to an intensive care unit) or those that are recurrent. Subjects who experience severe symptoms (eg, severe nausea, rhinorrhea, or pruritus) that are not life-threatening, not requiring intensive therapy, and not associated with any other features indicating a serious clinical condition, and who the investigator feels are suitable to continue with the study, will be discussed with the medical monitor and may continue the study under close supervision if both the investigator and the medical monitor deem it appropriately safe to do so
- 4. Dose-limiting symptoms that occur at or before the 3 mg single dose on Initial Escalation Day 1 (Treatment Pathways 3 and 5 only)
- 5. Dose-limiting symptoms that occur on Initial Escalation Day 2 (Treatment Pathways 3 and 5 only)
- 6. Nonadherence: For subjects on a daily dose regimen, missing > 7 consecutive dosing days on any 1 occasion or missing 3 consecutive dosing days on 3 or more occasions during Up-Dosing, other than for treatment of an AE or a dispensing error
- 7. Extended dosing interruptions: For subjects on a daily dose regimen, any circumstances, including medical indications that require missed AR101 dosing for ≥ 15 consecutive days, with the exception of the voluntary 30-day hiatus for GI AEs
- 8. On 1 episode, failure to accomplish up-dosing to 300 mg AR101 daily after 3 attempts (Treatment Pathways 2 and 3 only)
- 9. On 1 dose-reduction episode, failure to identify a tolerated dose of AR101 after 3 attempts at dose reduction

- ARC008 Protocol Amend 6.0
- 10. Administration of more than 2 doses of epinephrine for the treatment of any single AR101-related allergic reaction
- 11. Subject desires to receive commercially available product
- 12. The sponsor discontinues participation of subjects in the US from parent studies ARC002, ARC004, ARC007, and ARC011 who have access to commercially available product per protocol amendment 6.0

A subject who discontinues AR101 treatment early will return to the clinic for the End of Treatment visit. If a subject fails to return for scheduled visits, a documented effort must be made to determine the reason.

After protocol amendment 6.0 is approved at the study site, subjects in the US from parent studies ARC007 and ARC011 who have access to commercially available product will have the End of Treatment visit at their next scheduled study site (not remote) visit. Subjects in the US from prior studies ARC002 or ARC004 who have access to commercially available product may have the End of Treatment visit at their next scheduled study site (not remote) visit if so directed by the study sponsor when necessary for operational considerations.

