Subjects in Treatment Pathway 3, having just completed the Initial Escalation Period, will receive AR101 starting at a dose of 3 mg QD and escalate every 2 weeks to a maximum of 300 mg QD, according to the Up-Dosing Schedule (Table 5). The Up-Dosing Period can last from 22 to 52 weeks.

Those subjects who reach the target dose of 300 mg QD of AR101 will take this dose for 2 additional weeks as part of the Up-Dosing Period. Subjects who do not tolerate the 300 mg QD dose of AR101 for 2 weeks within 52 weeks (ie, must reach 300 mg dose within 50 weeks) after starting the Up-Dosing Period will discontinue dosing and complete the End of Treatment visit. Once a subject tolerates the 300 mg dose for 2 weeks in the Up-Dosing Period, the subject will then enter the Initial Maintenance Period and receive the 300 mg dose

for 24 weeks. To escalate to the next dose, a subject must be tolerating the current dose (Section 6.8.2). Some subjects may require de-escalation, and once the lower dose is tolerated they may again attempt increasing the dose.

Table 5: Up-Dosing Schedule (Treatment Pathway 3)

Dose Number	Investigational Product Dose, mg ^a	Interval (Weeks)	Percent Increase From Previous Dose
1	3	2	_
2	6	2	100
3	12	2	100
4	20	2	67
5	40	2	100
6	80	2	100
7	120	2	50
8	160	2	33
9	200	2	25
10	240	2	20
11	300	2	25

^a All mg doses shown refer to milligrams of peanut protein.

3.2.3.3 Treatment Pathway 5

After completing the Initial Escalation Period, subjects in Treatment Pathway 5 will receive AR101 starting at the 1 mg/day dose and dose escalation will occur every 2 weeks until the maximum daily dose of 300 mg is reached (Table 6). Subjects who tolerate the 300 mg/day dose for 2 weeks within 40 weeks after start of up-dosing will begin the Initial Maintenance Period. Subjects who do not tolerate the 300 mg/day dose for 2 weeks within 40 weeks after start of up-dosing will discontinue dosing and complete the End of Treatment visit.

Investigational Product Percent Increase From Dose Number Interval (Weeks) Dose, mga **Previous Dose** Not applicable

Table 6: Up-Dosing Schedule (Treatment Pathway 5)

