- Subjects who require dose reduction during a 2-week period between visits will have the escalation schedule reset as necessary to maintain the new dose level for a 2-week period prior to attempting to re-escalate.
- Following a dose reduction, it is advised that an escalation attempt be made within the next 4 weeks unless escalation is to be delayed further because of administration of epinephrine (Section 6.10). Failure to successfully escalate after 3 consecutive attempts, with each attempt spaced at least 2 weeks apart, will result in the discontinuation of dosing. The subject will have the End of Treatment visit (Section 7.2.5).

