7.5.3 Up-Dosing Period (Visits Every 2 Weeks for 24 to 40 Weeks)

During the Up-Dosing Period, the first dose at each new dose level will be administered in the clinic with visits every 2 weeks (± 3 days) up to 40 weeks.

Unscheduled visits may be conducted for assessment of dose tolerability, dose reduction, or dose re-escalation or management of AEs.

Subjects must be free from active wheezing, a flare of atopic disease (eg, atopic dermatitis), or suspected intercurrent illness before a dose is administered in the clinic. Subjects should be maintained on the current or a reduced dose level of AR101 until the active wheezing, flare of atopic disease, or intercurrent illness has resolved.

Subjects should withhold their daily home dose of AR101 on days the dose is administered in the clinic but should take all other prescribed medications as scheduled.

The following guidelines for dose escalation and reduction will be followed during the Up-Dosing Period:

- A dose escalation attempt may be postponed 1 to 2 weeks if the current dose level has not been sufficiently tolerated to proceed to the next dose level per investigator judgement.
- Further, if an investigator suspects that a subject has not tolerated or is not tolerating the current dose level, the investigator should have the subject return to the clinic to determine whether a dose reduction is warranted. Guidelines for dose reduction are outlined in Section 6.8, with the dose adjustment depending on the severity of symptoms related to dosing.
- Subjects who require dose reduction during a 2-week period between visits will have the escalation schedule reset as necessary to maintain the new dose level for a 2-week period before attempting dose re-escalation.
- A dose re-escalation attempt should be made within 4 weeks after a dose reduction, unless dose escalation is to be delayed further because of administration of epinephrine (Section 6.10). Failure to successfully escalate the dose level after 3 consecutive attempts with at least 2 weeks between each escalation attempt will result in the discontinuation of dosing. The subject will have the End of Treatment visit (Section 7.5.6).

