7.5.3.2 End Up-Dosing Visit

The following procedures will be performed before AR101 is administered in the clinic:

- TRACK questionnaire (for subjects aged 1 to < 5 years with asthma only; completed by the parent/caregiver)
- C-ACT (for subjects aged ≥ 5 years with asthma only) (complete before PEF)
- Weight, height
- Vital signs
- PEF (for subjects aged ≥ 4 years) (should be measured at approximately the same time of day at each visit assessment)
- Asthma evaluation (for subjects with asthma only)
- Abbreviated physical examination
- Food allergen exposure update
- Monitoring and recording of AEs, including allergy symptoms

- Concomitant medication review
- Diary log review (and dispensing of new diary log, if needed)
- Return of unused AR101
- AR101 dosing compliance check
- Completion of questionnaires:
 - FAQLQ and FAIM
 - FAQL-PB

After completion of these procedures, AR101 will be administered in the clinic as instructed in Section 3.2.3.2 and Section 5.2. Subjects will be monitored as instructed in Section 5.3.3.

The following procedures will be performed before discharge from the clinic:

- Monitoring and recording of AEs, including allergy symptoms
- Peanut allergy training
- AR101 dispensing
- Home dosing instruction (Section 5.2)

Site staff will contact the subject's parent/caregiver by telephone the next day (may be within 2 days if next day is not feasible) to monitor compliance with AR101 dosing, enquire if any AEs (including allergy symptoms, GI symptoms, and accidental/nonaccidental food allergen exposure) occurred after the subject left the clinic, and to provide assistance in recording and management of events.

7.5.4 Initial Maintenance Period (Visits Every 4 Weeks Until End of Initial Maintenance Visit)

During the Initial Maintenance Period, clinic visits will occur every 4 weeks ± 3 days until the End of Initial Maintenance visit, when the subject completes an overall total of approximately 12 months of treatment (including initial dose escalation, up-dosing, and maintenance treatment).

Subjects should withhold their daily home dose of AR101 on days the dose is administered in the clinic but should take all other prescribed medications as scheduled.

The guidelines for dose escalation and reduction are the same as for the Up-Dosing Period (Section 7.5.3).

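### The mandatory stop after three failed up-dosing attempts excludes Pathway 5 in Protocol 4.4.1 but includes it in 7.5.3, and the two places define a failed attempt differently

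*Protocol*

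**What the plan says.** Protocol 4.4.1 is the formal list of stopping criteria and is mandatory in force: "A subject who meets any of the following must discontinue dosing with AR101". Criterion 8 sets the stop for failed up-dosing within a single episode: "failure to accomplish up-dosing to 300 mg AR101 daily after 3 attempts (Treatment Pathways 2 and 3 only".

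Protocol 7.5.3 covers up-dosing in Pathway 5 (former placebo subjects from ARC005). It says: "Failure to successfully escalate the dose level after 3 consecutive attempts with at least 2 weeks between each escalation attempt will result in the discontinuation", meaning that AR101 treatment ends. It then sends the subject to the Pathway 5 version of the closing visit: "The subject will have the End of Treatment visit (Section 7.5.6").

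Sections 7.2.2 (Pathway 2) and 7.3.3 (Pathway 3) carry almost the same rule: "Failure to successfully escalate after 3 consecutive attempts, with each attempt spaced at least 2 weeks apart, will result in the discontinuation of dosing".

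Section 7.5.4 extends the Pathway 5 rule beyond up-dosing: "The guidelines for dose escalation and reduction are the same as for the Up-Dosing Period (Section 7.5.3").

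Section 3.2.3.3 sets a separate stop for Pathway 5, based on time: "Subjects who do not tolerate the 300 mg/day dose for 2 weeks within 40 weeks after start of up-dosing will discontinue dosing".

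**The concern.** The formal list leaves Pathway 5 out of the three-attempt stop, and the section that governs Pathway 5 visits puts it in. The word only makes the omission look intended. Criteria 4 and 5 of the same list name Pathways 3 and 5, so the list was written or updated with Pathway 5 in view.

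A site that uses 4.4.1 as its checklist and a site that works from 7.5.3 could handle the same child differently after a third failed attempt. These are young children: ARC005 enrols at ages 1 to under 4 years. Consistent handling of a mandatory stop is the main thing at stake.

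The statistical stake is secondary. The timing and recorded reason of a stop feed the summary of reasons for early treatment discontinuation (SAP 8.1) and the duration of exposure (SAP 9.11). They reach the primary endpoints on premature discontinuation (SAP 3.1) only if the stop is recorded as due to an adverse event, including a chronic or recurrent gastrointestinal one.

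**Working it through.** The plan states no figure to reproduce. The check is mainly a comparison of texts, followed by simple arithmetic on size.

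**1. Pathways covered**
- 4.4.1 criterion 8: Pathways 2 and 3.
- Section 7: Pathway 2 (7.2.2), Pathway 3 (7.3.3) and Pathway 5 (7.5.3).
- The two sets differ by Pathway 5.

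**2. Trigger**
- 4.4.1: the target is 300 mg daily, three attempts are counted within one episode, and neither consecutive attempts nor a minimum spacing is required.
- 7.2.2, 7.3.3 and 7.5.3: the target is a successful escalation, the three attempts must be consecutive, and they must be at least 2 weeks apart.
- In each Section 7 list the rule follows advice on re-escalating after a dose reduction. Criterion 8 has no such context.

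The difference in wording does not make these two separate rules with separate scopes, because 7.2.2 and 7.3.3 use nearly the 7.5.3 sentence for the two pathways that criterion 8 names. It is a second discrepancy, and it touches all three pathways.

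**3. Whether another provision settles it**
- Criterion 9 of 4.4.1 concerns failed attempts at dose reduction, not escalation.
- The 40-week limit counts time, not attempts. Three attempts at least 2 weeks apart span at least 2 × 2 = 4 weeks from first to third, so the 7.5.3 stop can fall well before week 40.
- SAP 2.4.2.3 repeats the 40-week limit but not the three-attempt rule.

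**4. Size**
- Inputs: about 132 subjects planned in ARC005, randomised 2:1 (Protocol 1.2.5); about 950 potential subjects in ARC008 (Protocol 3.5); Pathways 4 and 5 pooled as a subgroup for the overall adverse event summary (SAP 6.3); all pathways generally combined into one AR101 group (SAP 6.1).
- One subject in Pathways 4-5, if all 132 enrol: 1/132 = 0.76, or about 0.8 percentage points. This is a minimum, and fewer enrolled subjects would raise it.
- One subject in the combined group, if 950 enrol: 1/950 = 0.1 percentage points.
- Pathway 5 holds at most 132/3 = 44 subjects, so one subject there is 1/44 = 2.3 percentage points. No planned safety summary uses that denominator. The SAP separates Pathway 5 for baseline characteristics (8.3), the End of Treatment food challenge (10.1) and immunoglobulins (11.1), not for discontinuation rates.

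**5. Who is affected**
- A Pathway 5 subject who never tolerates 300 mg/day for 2 weeks must stop by week 40 under either reading. Only the timing and the recorded reason change.
- The outcome itself changes for a subject who would have succeeded after a third failure within the 40 weeks.
- It could also change for a subject in Initial Maintenance, who has already met the 40-week condition and to whom 7.5.4 applies the 7.5.3 guidelines.
- The documents give no estimate of how many subjects fall in either group.

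**The case against.** The best defence is that the sections do not give opposite instructions. Section 4.4.1 says that meeting a listed criterion requires a stop. It does not say that nothing else does. Other mandatory stops also sit outside the list:
- the 52-week and 40-week limits (3.2.3.2 and 3.2.3.3);
- the stop when a further reduced dose is not tolerated during up-dosing (6.9.3);
- the stop at a third consecutive epinephrine use during an escalation attempt (6.10).

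Section 3.2 refers sites to Section 7 for visit procedures. A site that reads both sections together would therefore apply 7.5.3 to Pathway 5.

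This stands as far as it goes. A reader might infer that 4.4.1 permits a Pathway 5 subject to continue after three failures. The documents do not support that: the restriction limits criterion 8 and grants no permission against 7.5.3. What the defence does not explain is why the formal list expressly leaves out a pathway that its own visit section covers, when neighbouring criteria name that pathway. Nor does it explain why a failed attempt is described differently for the two pathways that both places cover.

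The defence is also right that all analyses are descriptive, with no hypothesis test, so no formal inference is at risk.

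**Conclusion.** The inconsistency is real and worth correcting. It lies in a mandatory stopping rule and concerns both the pathways covered and the definition of a failed attempt. Whether, when and for what recorded reason a Pathway 5 child stops can depend on the section read.

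The effect on the analysis is small: about 0.8 percentage points per affected subject in the pooled Pathways 4-5 subgroup, assuming all 132 planned ARC005 subjects enter ARC008, and more if fewer do. The number of affected subjects is unknown.

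Two stronger readings are tempting and should not be drawn.
- A reader might quote 2.3 points per subject for Pathway 5 alone, but no planned safety summary reports that group separately.
- A reader might say that every such stop moves a primary endpoint. The premature-discontinuation endpoints count stops due to adverse events, so a stop for failed escalation enters only if it is recorded that way.

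The case for acting rests on consistent conduct in young children more than on any number.

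**What to change.** Reconcile criterion 8 of Protocol 4.4.1 with 7.2.2, 7.3.3 and 7.5.3 so that all four name the same pathways and use one definition of a failed attempt: the target dose, whether attempts must be consecutive, the minimum spacing, and what an episode is. State whether the rule is meant to apply in Initial Maintenance, since 7.5.4 imports 7.5.3. Which rule applies is for the clinical team to decide.

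The cost is a wording correction. No change to the sample size or the planned analyses is needed.

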4.4.2 Safety Follow-Up

A subject who discontinues AR101 treatment early or has ongoing AEs at the end of AR101 treatment will be followed up for safety for a minimum of 14 days after the last AR101 dose, 14 days after the last food challenge, or until resolution or stabilization of all AEs ongoing at the time dosing is stopped, whichever is later. In addition, a subject who discontinues AR101 because of chronic or recurrent GI AEs will be followed up monthly for a minimum of 6 months or until resolution or stabilization of all GI AEs (Section 8.1.4.2), whichever is longer.

If the investigator becomes aware of an SAE with a suspected causal relationship to AR101 that occurs within 30 days after the last AR101 dose in a subject treated by him or her, the investigator shall, without undue delay, report to the sponsor. Additionally, subjects who discontinued early from an eligible parent study due to AEs (including chronic or recurrent GI AEs) may continue safety follow-up in ARC008 as needed.

The Pediatric Eosinophilic Esophagitis Symptom Scores version 2.0 (PEESS v2.0) questionnaire (Franciosi, 2011) will be completed by subjects with GI AEIs as described in Section 8.1.4.2. Parents/caregivers will also complete the PEESS v2.0 as appropriate. Subjects who discontinue AR101 treatment early due to chronic/recurrent GI AEs will return to the clinic for evaluation monthly for at least 6 months. If the subject is asymptomatic, telephone follow-up with an investigator may substitute for in-clinic visit, at the investigator's discretion. If chronic/recurrent GI AEs persist beyond 6 months, subjects will continue to be followed up with monthly clinic visits (telephone follow-up with an investigator may substitute for in-clinic visit, at the investigator's discretion) until the symptoms resolved or are assessed as stabilized with optimal medical management, or the investigator considers them irreversible.

ARC008 Protocol Amend 6.0

Additional instructions for the follow-up of these subjects are provided in Section 8.1.4.2.

Safety follow-up procedures may be affected by a pandemic, epidemic, or other emergency not related to the study as described in Appendix 12.

